5.3.2. Postmenopausal Defined

A postmenopausal state is defined as no menses for 12 months without an alternative medical cause.

- A high FSH level in the postmenopausal range (as per the reference range used by the laboratory) may be used to confirm a postmenopausal state in women under 60 years old and not using hormonal contraception or HRT.
- Females on HRT and whose menopausal status is in doubt will be required to use one of the non-estrogen hormonal highly effective contraception methods described in [Section 10.4.3](#) if they wish to continue their HRT during the trial. Otherwise, they must discontinue HRT to allow confirmation of postmenopausal status before trial enrollment.

5.3.3. Sunlight Exposure

Participants will be advised to report any reaction to sun exposed skin. In addition, special precautions will be taken to limit any potential photo irritation effect, by minimizing the participants' exposure to light including high intensity UVB sources such as tanning beds, tanning booths and sunlamps. Participants should be encouraged to apply sunscreen/sunblock daily.

5.4. Screen Failures

Participants who do not meet the inclusion/exclusion criteria will not be permitted to participate in Amendment 6. See [Section 8](#) regarding screening evaluations.

6. STUDY INTERVENTION

Study intervention is defined as any investigational intervention(s), marketed product(s), placebo, medical device(s), or study procedure(s) intended to be administered to a study participant according to the study protocol.

For the purposes of this study, and per ICH guidelines, investigational product is defined as a pharmaceutical form of an active ingredient or placebo being tested or used as a reference in a clinical trial, including a product with a marketing authorization when used or assembled (formulated or packaged) in a way different from the approved form, or when used for an unapproved indication, or when used to gain further information about an approved use (ICH E6 1.33). For the purpose of this study, the study interventions are glasdegib and azacitidine.

6.1. Study Intervention(s) Administered

Intervention Name	Glasdegib	Azacitidine
ARM Name (group of participants receiving a specific treatment (or no treatment)	NA	NA
Type	Drug	Drug
Dose Formulation	Tablet	Powder for injection
Unit Dose Strength(s)	25 mg or 100 mg tablet	100 mg/vial powder for 25 mg/mL suspension for injection
Dosage Level(s)	50, 75 or 100 mg daily	75 mg/m ² /day for 7 days every 28 days, or per the local label, IP Manual (or SPC) or if dose modified
Route of Administration	Oral	IV or SC
Use	Experimental	Other
IMP or NIMP	IMP	NIMP
Sourcing	Provided centrally by the sponsor	In US and Germany drug is sourced by the sites. All other countries, the drug is sourced by the Sponsor.
Packaging and Labeling	Study intervention will be provided in HDPE bottles. Each bottle will be labelled as required per country requirement.	Study intervention will be provided in sealed single-use colorless type 1 glass vials. Each vial will be labelled as required per country requirement.
Current/Former Name(s) or Alias(es)	PF-04449913	NA

6.1.1. Administration

Both glasdegib and azacitidine are administered in 28-day cycles. Cycle duration maybe extended beyond 28 days to allow resolution of toxicities related to study treatments. It is suggested that sites contact the participant via phone anytime there is a dose reduction to confirm that the participant adequately understands the dosing instructions.

Glasdegib will be self-administered by the participant at home, unless otherwise specified. Glasdegib will be administered orally with approximately 8 ounces (240 mL) of water, at the same time each day. Tablets must not be crushed or cut; they must be swallowed whole, not manipulated or not chewed prior to swallowing. If a participant forgets to take their dose at the regularly scheduled time, and if fewer than 10 hours have passed since the scheduled dosing time, that dose should be taken as soon as possible. If more than 10 hours have passed since the scheduled dosing time, the dose should be skipped, and the participant should continue their normal dosing schedule. If a participant misses a day's dose entirely, they must be instructed not to "make it up" the next day. If a participant vomits any time after taking a dose, they must be instructed not to "make it up," but to resume subsequent doses the next day as prescribed. If a participant inadvertently takes 1 extra dose during a day, the

participant should not take the next dose of glasdegib. The participant will be reminded to bring their bottle(s) and participant dosing diary into clinic to evaluate dosing compliance.

Participants requiring glasdegib dose reduction(s) will be administered multiples of 25 mg tablets and should continue taking the glasdegib at the same time each day at the dose prescribed by the Investigator (ie, 75 mg QD and 50 mg QD in the form of three or two 25 mg tablets respectively). In situations where clinical benefit is observed, glasdegib can be reduced below 50 mg QD upon Sponsor approval.

Dose modifications are discussed in [Section 6.6](#).

Study intervention administration details will be recorded on the CRF.

6.1.2. Dosing Regimen

- Azacitidine will be administered 75 mg/m²/day for 7 days every 28 days on Days 1-7 (± 3 days) per local label or per the IP Manual (or SPC). Azacitidine may be administered by SC injection or IV infusion. Alternate dosing schedules to administer the 7 doses to accommodate participant and treatment center availability are allowed. The starting dose regimen will be the same as the most recent regimen received on the B1371019 or B1371012 study.
- Glasdegib 50, 75 or 100 mg will be orally administered daily and continuously. The starting dose regimen will be the same as the most recent regimen received on the B1371012 or B1371019 study.

Dose modifications are discussed in [Section 6.6](#).

6.1.3. Treatment Duration

Treatment with the study treatment should be continued until objective disease progression or relapse, death, unacceptable toxicity, or participant refusal, whichever occurs first.

If glasdegib is permanently discontinued for reasons other than objective disease progression, participant refusal, or consent withdrawal, single agent treatment with azacitidine may be continued if, in the Investigator's judgment, a clinical benefit has been observed and following discussion between the investigator and sponsor.

In cases of unacceptable toxicity or pregnancy, the participant must be withdrawn from study treatment.

6.2. Preparation/Handling/Storage/Accountability

1. The investigator or designee must confirm appropriate temperature conditions have been maintained during transit for all study interventions received and any discrepancies are reported and resolved before use of the study intervention.
2. Only participants enrolled in the study may receive study intervention and only authorized site staff may supply or administer study intervention. All study

PFIZER CONFIDENTIAL

interventions must be stored in a secure, environmentally controlled, and monitored (manual or automated recording) area in accordance with the labeled storage conditions with access limited to the investigator and authorized site staff. At a minimum, daily minimum and maximum temperatures for all site storage locations must be documented and available upon request. Data for nonworking days must indicate the minimum and maximum temperatures since previously documented for all site storage locations upon return to business.

3. Any excursions from the study intervention label storage conditions should be reported to Pfizer upon discovery along with any actions taken. The site should actively pursue options for returning the study intervention to the storage conditions described in the labeling, as soon as possible. Once an excursion is identified, the study intervention must be quarantined and not used until Pfizer provides permission to use the study intervention. Specific details regarding the definition of an excursion and information the site should report for each excursion will be provided to the site in the IP manual.
4. Any storage conditions stated in the SRSD will be superseded by the storage conditions stated on the label.
5. Study interventions should be stored in their original containers.
6. Site staff will instruct participants on the proper storage requirements for take home study intervention.
7. See the package insert, or SPC for storage conditions of the azacitidine once reconstituted and/or diluted.
8. The investigator, institution, or the head of the medical institution (where applicable) is responsible for study intervention accountability, reconciliation, and record maintenance (ie, receipt, reconciliation, and final disposition records), such as the IPAL or sponsor-approved equivalent. All study interventions will be accounted for using a study intervention accountability form/record. All glasdegib that is taken home by the participant, both used and unused bottles/tablets, must be returned to the investigator by the participant. Returned study intervention must not be redispensed to the participants.
9. Further guidance and information for the final disposition of unused study interventions are provided in the IP manual. All destruction must be adequately documented. If destruction is authorized to take place at the investigator site, the investigator must ensure that the materials are destroyed in compliance with applicable environmental regulations, institutional policy, and any special instructions provided by Pfizer.

Upon identification of a product complaint, notify the sponsor within 1 business day of discovery as described in the IP Manual.

6.2.1. Preparation and Dispensing

6.2.1.1. Glasdegib

Glasdegib will be supplied by Pfizer Worldwide Research and Development as 25 mg and 100 mg tablets for oral administration. Supplies will be labelled according to local regulatory requirements.

Glasdegib will be packaged in HDPE bottles and should be handled with care. Each bottle will contain enough medication for a 28 day cycle of daily dosing, plus an additional amount to cover the time between site visits. Participants should be instructed to keep their medication in the bottles provided and not transfer it to any other containers and return the bottles to the site at the next study visit. Site personnel must ensure that participants clearly understand the directions for self-medication.

Study intervention should be dispensed using the IRT system (IWR) that provides a confirmation report containing the participant identification number and DU(s) or container number(s) assigned by an appropriately qualified and experienced member of the study staff (eg, physician, nurse, physician's assistant, practitioner, or pharmacist) as allowed by local, state, and institutional guidance. The confirmation report must be stored in the site's files.

The study specific IRT reference manual will provide the contact information and further details on the use of the IRT system.

6.2.1.2. Azacitidine

Azacitidine 25 mg/mL powder for suspension for injection will be used in this study. Please refer to the local package insert (or SPC) or the IP manual for detailed formulation, preparation and IV and SC administration instructions.

Only qualified personnel who are familiar with procedures that minimize undue exposure to them and to the environment should undertake the preparation, handling, and safe disposal of chemotherapeutic agents.

If azacitidine is provided by sponsor, it should be dispensed using the IRT system that provides a confirmation report containing the participant identification number and DU(s) or container number(s) assigned by an appropriately qualified and experienced member of the study staff (eg, physician, nurse, physician's assistant, practitioner, or pharmacist) as allowed by local, state, and institutional guidance. The confirmation report must be stored in the site's files.

6.3. Measures to Minimize Bias: Randomization and Blinding

Randomization and blinding are not applicable to this protocol amendment. Participants on Study B1371019 will be unblinded prior to dosing on Amendment 6.

6.4. Study Intervention Compliance

The investigator's site must maintain adequate records documenting the receipt, use, loss, or other disposition of the drug supplies. At each dispensing visit (Cycle 2 Day 1, Cycle 3 Day 1, etc. or when there is a dose reduction), all unused or partially used bottles must be returned by participants to the Investigator. The number of tablets returned by the participant at the end of the cycle will be counted, documented and recorded.

The sponsor or designee will provide guidance on the destruction of unused investigational product (eg, at the site). If destruction is authorized to take place at the study site, the investigator must ensure that the materials are destroyed in compliance with applicable environmental regulations, institutional policy, and any special instructions provided by sponsor or designee and all destruction must be adequately documented.

For azacitidine, the site should complete the required dosage Preparation Record located in the Investigational Product Manual. The use of the Preparation Record is preferred but it does not preclude the use of an existing appropriate clinical site documentation system. The existing clinical site's documentation system should capture all pertinent/required information on the preparation and administration of the dose including the methodology used to calculate the participant body surface area. This may be used in place of the Preparation Record after approval from the Sponsor.

6.5. Concomitant Therapy

Concomitant medications will be assessed at screening and all clinic visits.

Concomitant treatment considered necessary for the participant's well-being may be given at discretion of the treating physician. If a participant is offered, in accordance with the prevailing local guidelines, a COVID-19 vaccine, **it should be permitted**. This would be recorded as a concomitant medication in the medical records and standard AE collection and reporting processes would be followed.

6.5.1. Restricted or Prohibited Concomitant Medications

The following medications are not allowed during the active study treatment period:

- Agents used to treat AML or MDS;
- Investigational agents; This exclusion **does not apply** to any COVID-19 vaccine.
- CYP3A4/5 Strong Inducers: A drug-drug interaction study in healthy participants with the strong CYP3A4 inducer, rifampin, resulted in a 70% decrease in plasma exposures (AUC_{inf}) and a 35% decrease in peak plasma concentration (C_{max}) of a single 100 mg oral dose of glasdegib. Therefore, coadministration of glasdegib and strong CYP3A4/5 inducers is not permitted. A comprehensive list of strong CYP3A4/5 inducers is provided in [Appendix 9](#). The Sponsor study team should be contacted if there is uncertainty whether a concomitant medication is contraindicated.
- CYP3A4/5 Moderate Inducers ([Appendix 9](#)): Avoid concomitant use of glasdegib with moderate CYP3A4 inducers. If use cannot be avoided, double the glasdegib

PFIZER CONFIDENTIAL

dose, as tolerated. After the moderate CYP3A4 inducer has been discontinued for 7 days, resume glasdegib dose taken prior to initiating the moderate CYP3A4 inducer.

The following medications have use restrictions during the active study treatment period:

- **CYP3A4/5 Inhibitors:** In a healthy volunteer study, ketoconazole, a potent CYP3A4/5 inhibitor, produced a 2.4 fold increase in plasma exposure and a 1.4 fold increase in peak plasma concentration of glasdegib. Therefore, a potential exists for drug-drug interactions with CYP3A4/5 inhibitors, and coadministration of glasdegib in combination with strong/ moderate CYP3A4/5 inhibitors is not recommended. Selection of concomitant medication with no or minimal CYP3A4/5 inhibition potential is recommended. Strong/moderate CYP3A4/5 inhibitors ([Appendix 10](#) or [Appendix 11](#)) should be used with caution and only if considered medically necessary. If a moderate/strong CYP3A4/5 inhibitor is to be initiated in addition to glasdegib, the guidance provided in [Appendix 6](#).
- **Drugs with a known risk of TdP:** Glasdegib has been shown to have the potential to prolong the QTc interval in preclinical studies. In the first in participant study as single agent, Grade 3 QTcF prolongation was observed at the highest doses tested (400 mg and 600 mg). While the glasdegib dose evaluated in this study is 100 mg, the concomitant administration of glasdegib and drugs with a known risk of Tdp should be avoided whenever possible. A list of such drugs is provided in [Appendix 12](#). Use of these drugs is not recommended unless there are no alternatives. If a TdP drug is to be initiated in addition to glasdegib the guidance provided in [Section 6.6.1](#) dose modifications for QT prolongation per [Table 3](#) must be followed.
- QT prolonging medications (without a risk of TdP) should be avoided whenever possible.
- Concomitant administration of multiple moderate/strong CYP3A4/5 inhibitors, TdP drugs, and/or QT prolonging medications (without a risk of TdP) is not recommended.

6.5.2. Permitted Concomitant Medications

6.5.2.1. Best Supportive Therapy

BST administration is permitted according to institutional guidelines for all participants on study. BST will be provided by the site and may vary depending on the participant's signs and symptoms, site current practice, and country practice. It includes medications and supportive measures that may palliate disease related symptoms, improve quality of life and treat bacterial, fungal or viral infections. BST may include:

- Blood transfusions;
- Platelet transfusions;
- Antibiotics;
- Antifungal agents;
- Antiviral agents.

6.5.2.2. Hematopoietic Growth Factors

Hematopoietic growth factors (eg, G-CSF, GM-CSF) may be used according to local practice and guidelines.

6.5.2.3. Antiemetic and Antidiarrheal Therapy

Participants should be pre-medicated with anti-emetics for nausea and vomiting before each dose of azacitidine in all cycles according to local practice and guidelines.

Primary prophylaxis of diarrhea is permitted at the Investigator's discretion. The choice of the prophylactic drug is up to the investigator assuming the drug is not contraindicated as described in [Section 6.5.1](#).

6.5.3. Surgery

Caution is advised on theoretical grounds for any surgical procedures during the study. The appropriate interval of time between surgery and glasdegib required to minimize the risk of impaired wound healing and bleeding has not been determined. Stopping glasdegib is recommended at least 7 days prior to surgery. Post-operatively, the decision to reinitiate glasdegib treatment is up to the Investigator with Sponsor approval and should be based on a clinical assessment of satisfactory wound healing and recovery from surgery.

6.5.4. HSCT

Participants who are eligible for HSCT will undergo HSCT per local standard of care.

For post disease remission HSCT, glasdegib will be interrupted at least 28 days before HSCT (date of stem cell infusion).

Glasdegib may be resumed 30-60 days post HSCT once there is ANC engraftment, no \geq Grade 2 ongoing GVHD, and no ongoing SAEs in the judgement of the investigator.

6.6. Dose Modification

Every effort should be made to administer the study drug treatment according to the planned dose and schedule.

In the event of Grade 3 or Grade 4 non-hematologic, study-treatment-related toxicity, dosing may be delayed and/or dose reduced. The glasdegib dose should be reduced 1 dose level at a time, in increments of 25 mg (75 mg QD, 50 mg QD, in the form of 3 or 2 x 25 mg tablets respectively). Glasdegib does not need to be delayed or dose reduced for hematologic, study-treatment-related toxicity.

Glasdegib may be interrupted or permanently discontinued for any reason as per GCP. Glasdegib should be permanently discontinued if:

interruptions are for more than 28 consecutive days when not required by the protocol (ie, HSCT period).

Dose escalations will not be allowed following glasdegib/placebo dose reductions. Dose modifications may occur in 3 ways:

Within a cycle: Dosing interruption until adequate recovery followed by dose reduction (if required) of glasdegib during a given treatment cycle.

Between cycles: The next treatment cycle may be delayed if toxicity from the preceding cycle persists.

In the next cycle: Dose reduction may be required based on toxicities experienced in the previous cycle.

When chemotherapy is given, a Cycle is determined by chemotherapy administration schedule. A Cycle is 28 days, but will be extended if there are dose delays or modifications in the chemotherapy backbone.

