6.6.1. Glasdegib

Glasdegib does not need to be delayed or dose reduced for hematologic toxicity deemed unrelated/unlikely related to glasdegib by the investigator.

Participants experiencing Grade 3 or 4 nonhematological toxicities potentially attributable to glasdegib should have their glasdegib treatment interrupted regardless of when it occurs in the cycle until the toxicity resolves or returns to baseline or \leq Grade 1, as described in [Table 2](#). If these parameters have not been met following >28 consecutive days of dose interruption, glasdegib should be permanently discontinued. If glasdegib treatment is permanently discontinued, participants may continue single agent treatment with azacitidine, if according to the investigator's judgment a clinical benefit has been observed, and following discussion between the investigator and the sponsor.

Appropriate follow-up assessments should be implemented until adequate recovery (toxicity resolves or returns to baseline) occurs.

Depending on when the adverse event resolved, treatment interruption may lead to the participant missing all subsequent planned doses of glasdegib within the cycle. If the AE leading to treatment interruption recovers within the same cycle, recommencement of dosing in that cycle is allowed. The need for a dose reduction at the time of treatment resumption should be based on the criteria outlined in [Table 2](#), unless specifically agreed otherwise following discussion between the investigator and the sponsor. If a dose reduction for glasdegib is applied in the same cycle, the participant may need to receive a new supply of drug. Glasdegib doses omitted for toxicity will not be replaced within that cycle (eg, cycles will not be prolonged beyond the 28 days to make up for any missed glasdegib doses during that cycle).

Glasdegib may be interrupted or permanently discontinued for any reason as per GCP. Glasdegib should be permanently discontinued if interruptions are for more than 28 consecutive days. In the event of glasdegib treatment interruption for reasons other than

treatment-related toxicity (eg, elective surgery) for a duration >28 days, the details of treatment resumption will be determined in consultation with the Sponsor.

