Dose reduction of glasdegib by 1 or, if necessary, 2 dose levels (Table 1) will be allowed depending on the type and severity of toxicity encountered. **NOTE:** In the specific situations where clinical benefit is observed, glasdegib can be reduced below 50 mg QD upon discussion with the sponsor. All dose modifications/adjustments must be clearly documented in the participant's notes and eCRF.

Once the glasdegib dose has been reduced, all subsequent cycles should be administered at that dose level, unless further dose reduction is required. Dose re-escalation is not allowed. Deviations from any of the dose modifications must be discussed and agreed with the sponsor Medical Monitor.

Table 1. Available Dose Levels

Glasdegib (mg QD)
100
75
50
25 *

* **NOTE:** If clinical benefit is observed, glasdegib may be reduced below 50 mg QD following Sponsor approval.

Dose modifications for treatment-related- non-hematologic toxicities (excluding QTc prolongation, muscle spasms, and myalgia) are outlined in Table 2.

Table 2. Dose Modifications for Non Hematologic Toxicities (Excluding QTc Prolongation, Muscle Spasms, and Myalgia)

Toxicity (NCI CTCAE version 4.03)	Glasdegib
≥ Grade 3 toxicity (nausea, vomiting, and/or diarrhea must persist at ≥ Grade 3 (despite maximal appropriate medical therapy) to require dose modification).	Hold glasdegib until toxicity has recovered to baseline or ≤ Grade 1. First episode: Decrease by 1 dose level Second episode: Decrease by 1 dose level Third episode: Permanently discontinue
Potential drug induced liver injury/Hy's Law (as defined in Appendix 5).	Interrupt glasdegib dosing. If an alternative cause is found, restarting of glasdegib at the same dose may be considered.
Confirmed drug induced liver injury/Hy's Law (as defined in Appendix 5).	Glasdegib should be permanently discontinued.

Participants will be closely monitored for potential cardiovascular symptoms per standard of care. Appropriate monitoring should include clinical examinations, vital signs, routine ECGs, and AE monitoring. In case of QTcF prolongation, concomitant conditions such as electrolyte imbalances, hypoxia, or use of medications affecting the QT interval should be ruled out and/or corrected. In case of clinically significant toxicities, glasdegib administration should be interrupted and the dose reduced as indicated in Table 3.

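### Protocol Sections 6.6 and 6.6.1 are inconsistent on glasdegib dosing for glasdegib-attributed hematologic toxicity and, secondarily, for Grade 3/4 non-hematologic toxicity

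*Protocol*

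**What the plan says.** **Hematologic toxicity.** Protocol Section 6.6 (Dose Modification) says: "Glasdegib does not need to be delayed or dose reduced for hematologic, study-treatment-related toxicity". Section 6.6.1 (Glasdegib) opens with: "Glasdegib does not need to be delayed or dose reduced for hematologic toxicity deemed unrelated/unlikely related to glasdegib by the investigator".

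**Grade 3/4 non-hematologic toxicity.** Section 6.6 says: "In the event of Grade 3 or Grade 4 non-hematologic, study-treatment-related toxicity, dosing may be delayed and/or dose reduced". Section 6.6.1 says: "Participants experiencing Grade 3 or 4 nonhematological toxicities potentially attributable to glasdegib should have their glasdegib treatment interrupted", and Table 2 in the same section says: "Hold glasdegib until toxicity has recovered to baseline or ≤ Grade 1", followed by a step down at the first and second episodes and permanent discontinuation at the third. For nausea, vomiting and diarrhea, Table 2 requires modification only if the event stays at Grade 3 or above despite maximal medical therapy.

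**Related text.** Section 6 defines the study interventions as glasdegib and azacitidine. Section 6.6.1 requires departures from the dose modifications to be agreed with the sponsor's Medical Monitor. Section 6.6.2 refers azacitidine modification to the package insert or IP Manual. SAP Section 6.2.3.6 tabulates dose reductions and interruptions due to AEs. SAP Section 6.3.1 tabulates treatment-emergent AEs leading to interruption, reduction or permanent withdrawal.

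**The concern.** Two passages one section apart attach the same exemption to different classes of hematologic event. Section 6.6 keys it to events that are related to study treatment, and Section 6.6.1 keys it to events that are not related to glasdegib. An investigator who attributes a cytopenia to glasdegib finds it exempt in the first passage and left out of the exemption in the second. For severe non-hematologic events the two passages use verbs of different strength and different causality triggers.

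Three things depend on this:

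- **Consequences of a hold.** Under Section 6.6.1, an interruption beyond 28 consecutive days leads to permanent discontinuation, and re-escalation after a reduction is not allowed.
- **What counts as a departure.** A site cannot tell when Medical Monitor agreement is needed if it cannot tell which text is the rule.
- **What the data mean.** Interruption and reduction counts are part of the tolerability description. In addition, Protocol Section 10.3.1 makes a laboratory abnormality a mandatory AE if it changes dosing in a way the protocol does not itself specify. Whether a hold for a glasdegib-related cytopenia is protocol-specified is exactly what the text leaves open, although other triggers in that section may still capture the event.

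**Working it through.** No arithmetic applies: the plan gives no figure on this point, and Protocol Sections 9.1 and 9.2 state that there is no hypothesis and no sample-size basis. The check is to take each kind of event and read both sections on it.

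**Inputs.** Section 6 (definition of study interventions), Section 6.6, the text of Section 6.6.1, and Table 2. All are current Amendment 6 text, not entries from the amendment history.

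**Step 1: scope of the Section 6.6 hematologic exemption.** Study treatment comprises glasdegib and azacitidine, so an event related to either drug, or to both, is covered.

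**Step 2: case by case.**

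| Event | Section 6.6 | Section 6.6.1 and Table 2 | Result |
|---|---|---|---|
| (a) Hematologic, attributed to glasdegib | No delay or reduction needed | Outside the exemption; no action stated | Differ |
| (b) Hematologic, azacitidine-related, unlikely due to glasdegib | No delay or reduction needed | No delay or reduction needed | Agree |
| (c) Hematologic, unrelated to either drug | Silent | No delay or reduction needed | No conflict |
| (d) Grade 3/4 non-hematologic, possibly due to glasdegib | Delay and/or reduction optional | Interrupt; Table 2 says hold, then step down | Differ |
| (e) Grade 3/4 non-hematologic, due to azacitidine only | Delay and/or reduction optional | Section 6.6.1 sentence not triggered | Scope differs |

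**Step 3: can other text resolve case (a)?** Table 2 is limited to non-hematologic toxicity. Table 3 covers QTc prolongation, and Table 4 covers muscle spasms and myalgia. Section 6.6.2 concerns azacitidine only. None of these says what applies to a glasdegib-attributed hematologic event.

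**Step 4: can other text resolve case (d)?** Read alone, "dosing may be delayed and/or dose reduced" permits a reduction without a hold, or no action. Section 6.6.1 says that such participants "should have their glasdegib treatment interrupted regardless of when it occurs in the cycle". No sentence states that Section 6.6.1 prevails over Section 6.6. The line that introduces Table 2 refers to treatment-related toxicity, which is closer to the Section 6.6 trigger than to the glasdegib-specific trigger in the Section 6.6.1 text. The causality condition therefore varies even within Section 6.6.1.

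**Result.** There is one attribution conflict, confined to case (a), and one difference of verb and trigger, in cases (d) and (e).

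**The case against.** The best defense is that Section 6.6 is an umbrella section with drug-specific rules beneath it. Its non-hematologic sentence speaks of dosing in general and does not name glasdegib. A permissive verb suits an introduction to rules that vary: Table 2 qualifies gastrointestinal events, QTc has its own table, and Table 4 leaves some choices to the investigator. A site that follows Section 6.6.1 never breaches Section 6.6. This carries weight and is why the non-hematologic point is secondary. It does not remove the point, because the precedence is not written down and the causality triggers still differ.

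On hematologic toxicity, both sentences say only that action is not needed. Neither orders nor forbids a hold, and both sections allow interruption for any reason consistent with GCP. A reader might infer that Section 6.6.1 requires a hold for glasdegib-related hematologic toxicity, so that sites must hold or not hold depending on the page they read. The text does not support that: Section 6.6.1 leaves such events out of its exemption and goes no further. The conflict arises by implication. It still stands, because the attribution qualifier in Section 6.6.1 would do no work for treatment-related events if the broader Section 6.6 exemption governed.

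It is also fair to say that the consequence for analysis is limited. The tables are descriptive, and the endpoint is all AEs and SAEs, which are recorded whether or not a dose is held.

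**Conclusion.** This is an internal inconsistency in a safety-relevant dosing instruction, of minor to moderate severity. The firm part is narrow: hematologic toxicity attributed to glasdegib is exempt from delay or reduction under Section 6.6 and outside the exemption in Section 6.6.1, with no other text to settle it. The weaker part is the optional wording in Section 6.6 against the hold in Section 6.6.1 and Table 2 for Grade 3/4 non-hematologic events, together with the differing causality triggers.

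Two wider readings should be resisted. A reader might infer that every glasdegib-treated participant with a relevant toxicity is affected; cases (b) and (c) show agreement or no conflict, so the hematologic point reaches glasdegib-attributed events only. A reader might also try to express the effect as a shift in the interruption percentage. The documents give maxima of 34 participants from B1371019 and 3 from B1371012, but no split by arm and no toxicity rates. One participant divided by an assumed group size would be true of any miscounted event and would not measure this discrepancy.

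The conclusion assumes that study-treatment-related in Section 6.6 carries its ordinary meaning under the Section 6 definition, that is, related to glasdegib, azacitidine or both.

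**What to change.** The sponsor should reconcile Section 6.6, the text of Section 6.6.1 and Table 2:

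1. One statement on glasdegib and hematologic toxicity that covers each attribution explicitly: glasdegib-related, azacitidine-related only, and unrelated.
2. For Grade 3/4 non-hematologic toxicity, either one verb and one causality trigger throughout, including the line that introduces Table 2, or a sentence saying which section governs.

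Which clinical rule should apply is for the sponsor to decide, and none is suggested here. The cost is protocol wording and notice to sites. The planned SAP tables do not change.
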